Appendix B: UF Health Shands/BMT Program Blood Product Support Guidelines – Adult 64	
Appendix C: AML Response Criteria According to European Leukemia Net (ELN).....	65
Appendix D: Protocol Version History / Summary of Changes.....	66

ABBREVIATIONS

AE	adverse event
AESI	adverse event of special interest
ALT	alanine transaminase (also SGPT)
AML	Acute myeloid leukemia
ANC	absolute neutrophil count
AST	aspartate transaminase (also SGOT)
BAL	bronchoalveolar lavage
BSA	body surface area
BSI	bloodstream infection
BUN	blood urea nitrogen
CBC	complete blood count
CG	cytogenetics
CML	Chronic myeloid leukemia
CMV	Cytomegalovirus
CNS	central nervous system
CR	complete remission
CRF	case report form
CT	Computed tomography
CTCAE	Common Terminology Criteria for Adverse Events
CTMS	clinical trials management system
CTO	Clinical Trials Office
DISC	Data Integrity and Safety Committee
DLT	dose-limiting toxicity
DNA	Deoxyribonucleic acid
ECOG	Eastern Cooperative Oncology Group
EOT	End of Treatment
FISH	fluorescence in situ hybridization
FC	flow cytometry
FLT3	FMS-like tyrosine kinase 3
GCP	Good Clinical Practice
HiDAC	High-dose cytarabine
HCT	Hematopoietic stem cell transplant
ICF	informed consent form
ICH	International Conference on Harmonization
IDH	Isocitrate dehydrogenase
IRB	Institutional Review Board
IFI	invasive fungal infection
IV	Intravenous

kg	kilogram(s)
LDH	lactic dehydrogenase
LFS	Leukemia-free survival
LOS	length of stay
LRTD	lower respiratory tract disease
MDS	Myelodysplastic syndrome
MRD	Minimal residual disease
NCI	National Cancer Institute
NGS	Next-generation sequencing
NSAE	non-serious adverse event
ORR	overall response rate
OS	overall survival
PB	Peripheral blood
PCR	Polymerase chain reaction
PD	progressive disease
PFS	progression free survival
PMO	Project Management Office
PI	principal investigator
PK	Pharmacokinetics
PO	By mouth
PR	partial remission
PRN	As needed
PS	performance status
RBC	red blood cells
RECIST	Response Evaluation Criteria In Solid Tumors
RR	Relapse rate
RFVI	Respiratory viral infection
SAE	serious adverse event
SNP	Single nucleotide polymorphism
SCR	Serum creatinine
SOC	Standard of care
SQ	Subcutaneous
SD	stable disease
SGOT	serum glutamic oxaloacetic transaminase (also AST)
SGPT	serum glutamic pyruvate transaminase (also ALT)
TNF α	tumor necrosis factor alpha
UF	University of Florida
UFHCC	University of Florida Health Cancer Center
ULN	upper limit of normal
US	United States

USA United States of America
WBC white blood cell

Rationale:	Various chemotherapy regimens have been used in the treatment of AML, and common agents used include anthracyclines and pyrimidine/purine analogs. Once complete remission is confirmed after induction chemotherapy, a common regimen for AML patients to receive is standard HiDAC chemotherapy consolidation (cytarabine \geq 1000 mg/m ² up to 3000 mg/m ² IV q12h on Days 1,3,5) x 3-4 cycles in the USA. Doses depend on age, renal function, performance status (PS) and institution/provider. UF Health Shands Hospital routinely uses HiDAC consolidation as above. Recently published results from two European trials showing that a modified HiDAC consolidation regimen (given on Days 1,2,3) reduced the duration of neutropenia and number of blood product transfusions in younger AML patients. ¹ Another recent publication of a retrospective study confirmed the result of reduced hematologic recovery and less days of hospitalizations between the two regimens in subjects 60 years or less, however they did not see a reduced number of blood products. ² Due to differences in induction treatment strategies and differences in patterns of health care systems it is not clear that similar benefits and reductions in health care resource utilization would be seen in patients treated in the US. Also, many patients with AML are diagnosed over the age of 60 years, and currently this abbreviated HiDAC consolidation has not been studied in the elderly population. In older patients cytarabine is given as 1000 mg/m ² IV q12h for 6 doses. In this trial, we will evaluate the safety of this abbreviated regimen in our AML patient population who are age 61 years or older, and try to reproduce the hematologic toxicity results seen in the younger population using standard practices here in the US. We would like to adopt this practice as a standard regimen if we are able to confirm the results of these aforementioned published trials. This would potentially decrease

	length of stay, infections, transfusions and other potentially-related complications for AML patients.
Objectives:	
Primary:
 
 • To determine the duration of neutropenia after consolidation chemotherapy with HiDAC 123 compared to matched historical controls who received HiDAC 135. Neutropenia is defined in days, as the first day of absolute neutrophil count (ANC) < 500 after chemotherapy to day of recovery [ANC > 500 (defined as first day above 500 if consecutive x 2)]. 
Secondary:
 
 • To define duration of thrombocytopenia after consolidation chemotherapy with HiDAC 123 compared to matched historical controls who received HiDAC 135. Thrombocytopenia is defined as the interval between the first day of platelets <50x10³/uL after consolidation chemotherapy to the first day of recovery (defined as first day of platelets >20x10³/uL if consecutive x 2 and not transfused). • To determine the safety of HiDAC 123 compared to standard HiDAC 135 in case controls by evaluating the differences in: 
 ○ duration of neutropenia and thrombocytopenia ○ incidence of documented infections (e.g., bloodstream infection (BSI), pneumonia, invasive fungal infection (IFI), Clostridium difficile infection (CDI), typhlitis, (see Appendix A) and rates of febrile neutropenia (defined as temperature \geq 38.3 C° once or \geq 38 C° for more than 1 hour and ANC less than 500/mm³ or expected to fall below 500/mm³ in next 48 hours) ○ number of RBC and platelet transfusions given per cycle will be recorded in units ○ readmission rates (incidence and reason for admission) and LOS recorded in days (total, including chemotherapy administration, and readmission days) ○ non-hematologic toxicity: focus on CNS/cerebellar and ocular as these are specific to high dose cytarabine, but will record incidences of any other grade 3-5 organ systems according to CTCAE v5 criteria.³

	
○ time to next treatment (next chemotherapy cycle, transplant, etc.; if chemotherapy was discontinued prior to planned date, what was the reason). 
Exploratory:
 
● Relapse rate (RR). Relapse rate defined as incidence of confirmed relapse by peripheral blood flow or bone marrow biopsy results. Patients will be monitored up to 48 months after starting induction and will be reported if available.● Overall survival (OS) and leukemia-free survival (LFS). Overall survival defined as the time from date of complete remission (CR) to death from any cause. Leukemia-free survival defined as time from CR to AML relapse or death, whichever comes first. Cause of death will be recorded. Patients will be monitored up to 48 months after starting induction and will be reported if available.● Examine minimal residual disease (MRD) positivity after recovery from induction prior to study entry. The following modalities on bone marrow biopsy and aspirate will be used: flow cytometry (FC), karyotyping utilizing cytogenetics (CG), and fluorescence in situ hybridization (FISH). Patients with evidence of disease by any technique above will be classified as being MRDpos, FC will be performed on bone marrow specimens using monoclonal antibodies either as a large panel if the patient was newly evaluated or as a limited but targeted panel based on previously known patient-specific leukemia immune phenotype. MRD will be reported as a percentage of CD45 positive white blood cells (WBCs) and will be labeled MRDpos if leukemic cells account for $\geq 0.1\%$ of the analyzed total WBCs. CG will be performed using standard G-banding methods on 20 metaphase cells. FISH will be reported as a percentage of abnormal nuclei among the examined 300 interphase nuclei. MRDpos by CG will be defined as abnormal karyotype seen in at least two metaphase cells, or less than two cells if it was a previously known abnormality for the given patient. FISH positivity of a prior known abnormality will be labeled MRDpos.⁴● Pharmacogenomics: [name] group has developed an Ara-C SNP score (ACSS) consisting of 4 SNPs that is predictive of intracellular leukemic cell ara-CTP levels and thus impacts toxicity and efficacy to cytarabine containing regimens.⁵ We will genotype SNPs of relevance (already established in [name]
--	--

	lab) and based on the ACSS score classify into two groups having ACSS score ≥ 0 or <0). ACSS score will be evaluated for association with certain endpoints (duration of neutropenia, thrombocytopenia, RR and OS). Peripheral blood samples will be collected and analyzed through [name] lab at the University of Florida and NGS results will be used to calculate the ACSS score.
Study Design:	This is a non-randomized, open-label, single group phase II study for the prospective arm. These subjects will be compared to matched historical controls who received Day 135 consolidation for the primary and secondary objectives. Historical controls will be matched with prospective subjects for age (+/- 3 years), gender (male or female), Karnofsky PS (90-100/70-80/50-60), and number of HiDAC cycles received.
Accrual Goal:	A total of 29 subjects in HiDAC 123 arm. Data collected from these subjects will be compared to data from 29 matched historical controls who received standard HiDAC 135 consolidation.
Inclusion Criteria:	
Individuals eligible for study participation must meet the following criteria:
 
 A. Both males and females ≥ 61 years of age B. A clinical diagnosis of de novo, non-M3 acute myeloid leukemia (AML) confirmed by greater than 20% blasts in peripheral blood or on diagnostic bone marrow biopsy who have completed intensive induction chemotherapy and are confirmed in complete remission #1 (defined by < 5% myeloblasts on recovery BM biopsy (ANC $> 1000/\mu\text{L}$ and platelets $> 100 \times 10^3/\mu\text{L}$) and able to receive HiDAC consolidation #1. C. Patients on the prospective arm must be willing to have labs/clinic visits at UF Health Shands after discharge from chemotherapy approximately every 48 hours +/- 24 hours until neutrophil and platelet count recovery after each chemotherapy cycle per standard of care to be included. 
 - If prospective subjects cannot be followed at the UF site then telephone visits are allowed to follow for toxicity and transfusions. Records can be requested from subject's local physician office.

	
D. Written informed consent obtained from the subject and the subject agrees to comply with all the study-related procedures as stated above. For subjects on the historical arm, there will be a waiver of informed consent (as these patients may be deceased or not be available for retrospective consent).

Exclusion Criteria:	
Subjects with any of the following will not be eligible for study participation:
 
 A. Age < 61 years B. Patients unable to provide informed consent for prospective arm C. Secondary AML (documented history of antecedent hematological disorder, such as myelodysplastic syndrome or therapy-related AML) or CML in blast crisis D. Patients receiving, received, or who will receive a FLT3 inhibitor E. Patients receiving, received, or who will receive an IDH1 or IDH2 inhibitor F. SCr greater than 2 mg/dL G. Karnofsky PS of 40 or less at study entry H. History of any other disease, metabolic dysfunction, physical examination finding, or clinical laboratory finding giving reasonable suspicion of a disease or condition that contraindicates the use of protocol therapy or that might affect the interpretation of the results of the study or that puts the subject at high risk for treatment complications, in the opinion of the treating physician I. Prisoners or subjects who are involuntarily incarcerated, or subjects who are compulsorily detained for treatment of either a psychiatric or physical illness J. For historical arm, subjects will be excluded if adequate data is not available in electronic medical record (e.g., if patient was followed by their local oncologist between chemotherapy cycles and labs/transfusions/clinic notes, etc. are not available)

Efficacy Assessments:	
Duration of neutropenia after consolidation chemotherapy is primary efficacy endpoint. Neutropenia is defined in days, as the interval between the first recorded day of ANC < 500 after chemotherapy started to recovery [ANC > 500 (recorded as first day above 500 if consecutive x 2)]. Primary analysis will be with first consolidation cycle; however, data will be collected for all consolidation cycles up to six months after starting consolidation.
 
Duration of thrombocytopenia will be a secondary efficacy endpoint. Thrombocytopenia is defined as interval between the first recorded day of platelets < 50x10³/uL after consolidation to recovery (recorded as first day of platelets > 20x10³/uL if consecutive x 2 and not transfused within the past 7 days). Analysis will be with first consolidation cycle; however, subjects will be monitored for up to six months after start of consolidation.

Statistical Considerations:	
Group sample sizes of 23 subjects from a prospective cohort and 23 subjects from historical baseline group will achieve 81% statistical power to reject the null hypothesis of equal means when the population mean difference in neutropenia duration is three days (16 vs 19 days) with a standard deviation for both groups of four days and statistical significance level (alpha) of 0.05 using a one-sided, two sample, equal-variance t-test. Including a 20% drop out rate, we will accrue 29 subjects per cohort.
 
The primary outcome will be analyzed using one-sided t-test with equal variance or the corresponding non-parametric statistical method, depending on the validation of the assumptions.

Estimated Enrollment Period:	36 months
Estimated Study Duration:	60 months

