6. STUDY PROCEDURES

Written informed consent must be obtained prior to performing any study-specific evaluations or tests. Tests or evaluations performed as standard of care within the specified screening period, but prior to informed consent, may be accepted for this study and need not be repeated. Screening measurements below will be obtained within 60 days prior to registration into the study. **After registering a subject into this study, study treatment must begin within 30 days or subject will need to be re-screened:**

- Demographic data, including date of birth, gender, race, ethnicity and zip code
- Medical history, including h/o MDS or other conditions that could cause secondary or treatment-related AML or other conditions that may have major psychiatric or medical illness(es) that may impact if subject able to consent or be monitored for cerebellar toxicity
- Previous diagnostic assessments and treatment(s) for AML including regimens and dates
- Medications that may exclude subject (such as FLT3 inhibitors, e.g. midostaurin, sorafenib, gilteritinib, or any investigational FLT3 inhibitor as well as IDH1 and IDH2 inhibitors, e.g., ivosidenib, enasidenib or any investigational IDH inhibitor
- Bone marrow aspirate and/or biopsy for clinical classification, flow cytometry, cytogenetic classification, molecular markers, NGS for identification of commonly tested mutations in AML at diagnosis and at hematologic recovery after induction chemotherapy

- Hematology laboratory evaluations:
 - Complete blood count (CBC) including hemoglobin, hematocrit, white blood cell (WBC) absolute with differential, and platelet count
- Blood chemistry laboratory evaluations: serum creatinine
- Blood transfusions, growth factors, anti-infective medications, eye drops

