12.2 Sample Size Justification

This is a prospective single group study to determine the duration of neutropenia after consolidation chemotherapy with HiDAC 123. A historical control group will be selected by identifying patients who received cytarabine 1000 mg/m² IV q12h D135 from 2/1/2017-

2/1/2019 by propensity matching factors: age (+/- 3 years), gender (male or female), Karnofsky PS (90-100/70-80/50-60), and number of HiDAC cycles. The hypothesis is that patients with HiDAC123 treatment schema have a shorter duration of neutropenia after consolidation chemotherapy, compared to matched historical controls who received HiDAC 135. Group sample sizes of 23 subjects from a prospective cohort and 23 subjects from historical baseline group will achieve 81% statistical power to reject the null hypothesis of equal means when the population mean difference in neutropenia duration is three days (16 vs. 19 days) with a standard deviation for both groups of four days and statistical significance level (alpha) of 0.05 using a one-sided, two sample, equal-variance t-test. Including 20% drop out rate, we will accrue 29 subjects per cohort.

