12.3 Analysis of Primary Endpoint

When the required assumptions are met, duration of neutropenia will be analyzed by a one-sided, two sample, equal-variance t-test. If the normal distribution and equal variance are not validated, the corresponding non-parametric method will be used. Primary analysis will be for cycle 1 of consolidation only. Other cycles will be recorded and use descriptive statistics. Further, multivariable linear regression model of the neutropenia in days with group as the primary independent variable of interest will be fitted, while adjusting for some potential confounding variables, including AML type (WHO and FAB), documented infection in consolidation #1 (yes or no), ELN risk category (favorable, intermediate, high) and MRD positivity (yes or no), WBC at diagnosis (<50,000 or \geq 50,000), delay between induction course and consolidation #1 (less than or more than 40 days), allogeneic HCT (yes or no).

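### Time from induction to count recovery, the nearest baseline analogue of the primary outcome, is not matched on and not in the primary test; it enters only through a 40-day split of delay in the supportive regression

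*Combined protocol and SAP*

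**What the plan says.** The study compares a prospective HiDAC 123 cohort with historical HiDAC 135 controls treated between 2/1/2017 and 2/1/2019 (Sections 3.1 and 12.2). Controls are to be "matched with prospective subjects for age (+/- 3 years), gender (male or female), Karnofsky PS (90-100/70-80/50-60), and number of HiDAC cycles received" (Synopsis, Study Design; the same four factors are in Sections 3.1 and 12.2).

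Section 12.3 makes an unadjusted one-sided two-sample t-test on cycle 1 the primary analysis, with a non-parametric fallback. A further multivariable regression then adjusts for several possible confounders. The one closest to this point is "delay between induction course and consolidation #1 (less than or more than 40 days". Time from induction to recovery appears in neither the matching nor the covariate list, and no between-cohort comparison of it is planned.

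The dates needed to derive it are largely implied:
- Section 6 collects, at screening, "Previous diagnostic assessments and treatment(s) for AML including regimens and dates".
- Section 2.3.2 and the Synopsis start the survival clock at remission: "Overall survival defined as the time from date of complete remission (CR) to death from any cause". Section 2.3.1 describes survival outcomes for each cohort.
- Section 4.2 defines first CR by fewer than 5% blasts on the recovery marrow with ANC above 1000 and platelets above 100.
- The delay covariate itself needs an induction date for every subject in the model, controls included.

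Footnote 3 of the schedule of events (Section 6.1) requires the screening marrow within 30 days after induction starts, and that marrow must already show CR1 with recovered counts.

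**The concern.** The primary outcome is speed of neutrophil recovery after intensive cytarabine. The same patient's recovery after induction is the closest thing to a baseline measurement of that outcome, and the consolidation schedule cannot have influenced it. Section 1.3 itself says recovery depends on patient factors such as age and the amount of earlier treatment; of these two, only age is matched. Baseline counts cannot stand in, because eligibility requires everyone to have recovered and says nothing about how long it took.

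The planned delay term contains recovery time, but also scheduling time, and it is cut into two groups. A cohort difference in inherent recovery speed could therefore pass for a schedule effect, or mask one, with little in the plan to bring it to notice.

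Footnote 3 gives such a difference a possible route. Read literally, it admits to the prospective arm only patients in CR within 30 days of starting induction. Nothing says whether controls face the same limit. If they do not, the cohorts are selected differently on this very variable, in the direction that favours HiDAC 123.

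**Working it through.** **Inputs from Section 12.2.** "Group sample sizes of 23 subjects from a prospective cohort and 23 subjects from historical baseline group"; "population mean difference in neutropenia duration is three days (16 vs. 19 days" as the target; SD 4 days in both groups; "statistical significance level (alpha) of 0.05 using a one-sided, two sample, equal-variance t-test"; 20% dropout.

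**Reproducing the plan's figure.** The standard error of the difference is 4 × √(2/23) = 1.18 days. The noncentrality is 3/1.18 = 2.54 on 44 df, and the one-sided critical value is 1.680. The exact noncentral t gives 80.5% power; the normal approximation gives 81.6%. The plan says the design "will achieve 81% statistical power to reject the null hypothesis of equal means", so the figure reproduces. Accrual is 23/(1 − 0.20) = 28.75, that is 29 per cohort, as stated. The test reaches significance at an observed difference of about 1.680 × 1.18 = 2.0 days.

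**Effect of a cohort shift on the unadjusted t-test.** Suppose the schedule has no effect, but mean neutropenia differs by b days because one cohort recovers faster. The noncentrality is b/1.18 at 23 per group. With 29 per group the standard error is 4 × √(2/29) = 1.05. The values of b are assumed.

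| b (days) | Share of 3-day target | Chance of significance, 23 per group | 29 per group |
|---|---|---|---|
| 0 | 0 | 5% | 5% |
| 0.5 | 17% | 11% | 12% |
| 1.0 | 33% | 21% | 24% |
| 1.5 | 50% | 35% | 41% |
| 2.0 | 67% | 51% | 59% |

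One way to reach b = 0.5 to 1.0: a 2-day cohort difference in induction recovery, with 0.25 to 0.5 day of consolidation neutropenia per day of induction recovery (2 × 0.25 = 0.5; 2 × 0.5 = 1.0). Both inputs are assumptions. A 1-day shift the other way would shrink a true 3-day effect to 2 days, for which power is 51%.

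**What a two-group split removes.** In a simulation with a 0.5 SD shift in a normally distributed recovery time, adjusting for a binary split of that variable left 38%, 49% or 65% of the bias when 60%, 23% or 11% of subjects lay above the cut. This assumes that recovery time itself is split. The planned term splits a delay that also contains scheduling time, so it would probably remove less.

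**How informative a balance check would be.** For a 2-day difference in induction recovery time, 23 per group, two-sided 5%, with the variable's SD assumed:

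| Assumed SD (days) | Power | 95% CI half-width = 2.015 × SD × √(2/23) |
|---|---|---|
| 4 | 38% | 2.4 days |
| 6 | 20% | 3.6 days |
| 8 | 13% | 4.8 days |

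The check can raise a warning but cannot certify that the cohorts are comparable.

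**The case against.** The other side has several good arguments, and most of them limit the point.

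- *The variable is not wholly ignored.* The delay term contains recovery time, the regression also adjusts for ELN risk and MRD, and its list of confounders is open-ended. This stands: the accurate statement is that recovery time is absent from the matching and the primary test, and only indirectly present in a supportive model.
- *Changing a regression covariate does not repair the t-test.* This stands. The error rates above belong to the primary test and remain after the fix. A reader might infer that the covariate would also raise the trial's power. The documents do not support that: the primary test is unadjusted, and any gain in the supportive model depends on correlations they do not give.
- *Availability in controls is inferred.* This stands in part. No section lists the data to be collected for controls, and long-term outcomes are reported only where obtainable. The 48-month clock runs from the start of induction, which need not be the last course in a patient who was re-induced. Even so, the delay covariate and the CR-based survival outcomes presuppose both kinds of date.
- *The variable is imperfect.* This stands. It is dated by the recovery marrow, depends on platelets and blast clearance, and uses ANC above 1000, whereas the endpoint uses 500. It also reflects induction regimen, number of courses and any growth factor.

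A tempting stronger reading treats the variable as a decisive negative control, so that any difference proves the primary result biased. Given those influences and the low power shown above, that does not follow, and a null finding would be equally inconclusive.

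**Conclusion.** The point holds as a gap in the supportive analysis and in the evidence of comparability. The best available baseline analogue of the outcome is represented only by a dichotomised proxy, in a non-randomised comparison whose primary test is unadjusted. For illustration, a shift of one sixth to one third of the target effect (0.5 to 1 day) takes the one-sided error of that test to 11% to 21% at 23 per group. This rests on SD 4 from the plan and on shifts that are assumed; the documents give neither the imbalance nor the correlation between induction recovery and cycle 1 neutropenia. It shows sensitivity and is not an estimate of actual bias. Nor do the documents show that the cohorts do differ. Footnote 3 makes the question more pressing, but whether it applies to controls is unstated.

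**What to change.** 1. In Section 12.3, record for both cohorts the start of the last induction course and the date of documented CR counts, and state explicitly that this applies to controls.
2. In the supportive regression, enter days from induction to recovery as a continuous covariate in place of the 40-day indicator (one degree of freedom for one). Where the CR date is not available, keep the induction-to-consolidation delay, but as a continuous term.
3. Report the between-cohort difference in induction-to-recovery time with a 95% CI beside the primary result, read together with induction regimen and number of courses. Prespecify that a difference is a caution against attributing the result to schedule alone, and that the absence of one is not proof of comparability.
4. Reconcile footnote 3 of Section 6.1 with the selection rules for historical controls.

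The cost is SAP wording, one derived variable and some chart review for controls; no visits, subjects or model terms are added. The downsides are the variable's dependence on marrow timing, platelets and induction regimen, and the loss of whatever else the delay term captured. The error rate of the primary t-test stays as it is.
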